1.2.3 Levonorgestrel

Norgestrel and its active (-)-isomer, levonorgestrel, are progestogens derived from nortestosterone. They are more potent inhibitors of ovulation than norethisterone and have androgenic activity. Levonorgestrel is more commonly used than norgestrel and is twice as potent. Both are used as hormonal contraceptives. The typical daily levonorgestrel dose is 30 or 37.5 µg when used as an oral progestogen-only contraceptive, 100 to 250 µg when used for the monophasic portion of combined oral contraceptives, and 50 to 125 µg when used in triphasic preparations. Levonorgestrel is also used as a long-acting progestogen-only contraceptive by subcutaneous implantation. An intrauterine device containing levonorgestrel is available for contraception or menorrhagia. For emergency contraception, levonorgestrel may be given alone or in combination with ethinylestradiol.

Progesterone and the progestogens may cause gastrointestinal disturbances, changes in appetite or weight, fluid retention, oedema, acne, chloasma (melasma), allergic skin rashes, urticaria, mental depression, breast changes including discomfort or occasionally gynaecomastia, changes in libido, hair loss, hirsutism, fatigue, drowsiness or insomnia, fever, headache, premenstrual syndrome-like symptoms, and altered menstrual cycles or irregular menstrual bleeding. Anaphylaxis or anaphylactoid reactions may occur rarely (<0.01%).

Levonorgestrel is rapidly and almost completely absorbed after an oral dose and undergoes little first-pass hepatic metabolism. Maximum plasma concentrations occur 1 to 2 h after oral administration. Levonorgestrel is highly bound to plasma proteins, with 42 to 68% bound to sex hormone binding globulin and 30 to 56% bound to albumin. The proportion bound to sex hormone binding globulin is higher when levonorgestrel is given with an oestrogen.

Levonorgestrel is metabolised in the liver to sulfate and glucuronide conjugates, which are excreted in the urine (40 to 68% of dose) and to a lesser extent in the faeces (16 to 48% of dose). Levonorgestrel distributes into breast milk. The terminal half-life of levonorgestrel is approximately 25 h ([R12-0034](#)).

A commonly used immunosuppressive agent, mycophenolate, may have a drug-drug interaction with levonorgestrel. Therefore concomitant use of mycophenolate is restricted, because it may have an effect on the PK.

For a more detailed description of levonorgestrel, please refer to the SmPC of Microgynon[®], which will be provided in the ISF.

1.3 RATIONALE FOR PERFORMING THE TRIAL

Nintedanib is currently being developed for the treatment of systemic sclerosis associated ILD, a disease that also concerns women of child bearing potential. Two exploratory reproductive toxicity studies in rats revealed a teratogenic effect of nintedanib with a steep dose / effect relationship and an early onset of embryofetal deaths at low dosages. It may be expected that nintedanib is potentially teratogenic in humans.

According to the EMA guideline on the investigation of drug interactions ([P15-06991](#)) “a potential human teratogen” needs to be studied *in vivo* for effects on contraceptive steroids if the drug is intended for use in fertile women, regardless of the *in vitro* induction study results”. This trial will be performed to fulfil requirements of the EMA guideline.

1.4 BENEFIT - RISK ASSESSMENT

1.4.1 Nintedanib

Initiating and amplifying events in SSc-ILD and IPF are described to be different, but culminate in fibroblast activation and myofibroblast accumulation that represent the final common pathways of lung fibrosis in both SSc-associated ILD and IPF ([P14-07919](#)).

Nintedanib inhibits migration, proliferation and transformation of fibroblasts and thereby addresses this common pathway.

As shown for IPF patients, patients with SSc-ILD may also benefit from lesser decline in lung function and hence slower disease progression as a result of treatment with nintedanib.

The safety profile and the tolerability of nintedanib are expected to be similar in patients with IPF and SSc-ILD. However, specific SSc-related sensitivities are considered by specific in/exclusion criteria for this trial.

Based on the efficacy and safety shown in IPF patients, and considering the similarity of the pharmacological rationale between IPF and SSc, the same dose regimen of 150 mg nintedanib b.i.d. is considered appropriate.

The risks of treatment with nintedanib have been well delineated in patients with the fibrotic lung disease IPF. These risks (potential side effects) of nintedanib are described in Section [1.2.1](#), subsection “Data from clinical studies”.

Concomitant therapies with a known overlap in side effects with nintedanib (e.g. gastrointestinal (GI) adverse events, increase of AST, ALT, bilirubin) or concomitant use of therapies that interact with metabolism of nintedanib (through the uridine glucuronosyltransferase 1A1 gene UGT1A1 and P-gp) should be avoided or used with caution and patients should be closely monitored (see Section [4.2.2.2](#)).

Potential risks of nintedanib treatment also include gastrointestinal perforations, thromboembolism and bleeding. Therefore, patients who have planned major elective surgery suffer from severe peripheral vascular disease, requiring full dose therapeutic anticoagulation, fibrinolysis or high-dose antiplatelet therapy will be excluded from this trial. Patients with severe pulmonary hypertension will be excluded. Echocardiography is used to monitor patients with mild to moderate pulmonary hypertension.

The mode of action of nintedanib indicates a high potential for teratogenicity and embryotoxicity, including fetotoxicity and lethality. Therefore, in accordance with the current SmPC for Ofev® (nintedanib), women of childbearing potential who will be treated with nintedanib must use adequate contraception during and at least 3 months after the last dose of nintedanib and also barrier methods as second form of contraception in order to avoid pregnancy. As described in Section [1.3](#), the effect of nintedanib on the metabolism and efficacy of hormonal contraceptives is not known yet and will be investigated in this trial as recommended by the EMA. All trial participants will receive the oral contraceptive Microgynon® (levonorgestrel and estradiol) as trial medication to investigate the possible drug-drug interaction with nintedanib. Therefore, only non-hormonal contraceptives in combination with barrier methods are allowed to be used by WOCBP who are enrolled in this trial, as described in inclusion criterion 3, Section [3.3.2](#).

To address the organ-specific manifestations, immunosuppressive agents (e.g. mycophenolate, cyclophosphamide, methotrexate, azathioprine, prednisone) are commonly used and need to be considered although appropriate randomised-controlled data for these therapies are lacking.

To address current practice, patients without immunosuppressive background therapy as well as patients on a stable background therapy of methotrexate will be eligible for the trial. For

other immunosuppressive agents, specific washout criteria apply since they are not allowed in the trial (see Section [4.2.2](#)).

Non-immunosuppressant therapies for other SSc manifestations as for digital ulcers (e.g. bosentan, sildenafil), GI symptoms (e.g. proton pump inhibitors, prokinetic drugs), renal crisis (e.g. angiotensin-converting-enzyme inhibitor (ACE inhibitors), pulmonary hypertension PH / pulmonary arterial hypertension PAH (e.g. bosentan, sildenafil, epoprostenol) are not restricted. Cautionary notes are included in the protocol (Section [4.2.2.2](#)) with regard to such therapies whose safety profile could interfere with that of nintedanib.

Safety will be monitored at site visits, including physical examinations, safety laboratory and specific monitoring procedures, to follow-up potential hepatic enzyme elevation, to exclude pregnancy, to follow-up on electrocardiographic assessments, monitoring of renal function, hypertension and digital ulcers.

In patients who develop severe symptoms of gastrointestinal toxicity not amenable to symptomatic treatment with standard measures or severe liver enzyme elevations or other severe adverse events as specified in Section [3.3.4](#), treatment with nintedanib must be discontinued and appropriate therapeutic measures taken.

Overall, the extrapolated benefit-risk ratio of chronic treatment of patients with SSc-ILD with nintedanib 150 mg b.i.d. to be reduced to nintedanib 100 mg b.i.d., interrupted or discontinued during periods of intolerability, is judged positive.

The patients will not receive any additional benefit from participation in this trial, but are exposed to the risks of the trial procedures and the known risks of the trial medications. However, their participation in this trial may help guide the safe use of nintedanib together with ethinylestradiol / levonorgestrel in patients requiring this treatment. Patients who did not discontinue nintedanib treatment and will be rolled-over to Trial 1199.225 may have additional benefit from continuous nintedanib treatment.

1.4.2 Microgynon

Microgynon[®] has been used for over 10 years and is generally well tolerated ([R11-0382](#), [R11-0385](#)). The intake of combined oral contraceptives is associated with an increased risk of serious side effects such as cardiovascular diseases (myocardial infarction, cerebrovascular insult, venous thromboembolism) and breast and liver tumours. The incidence of venous thromboembolic events is 5-10 per 100,000 women in 1 year, if no hormonal contraceptives are used. The incidence is increased to about 20/100,000 after intake of 2nd generation combined oral contraceptives (containing levonorgestrel, e.g. Microgynon[®]). In contrast, the intake of 3rd generation combined oral contraceptives (containing gestoden or desogestrel) is associated with a higher risk (up to 40/100,000) of thromboembolic events ([R12-0034](#)).

The most frequent side effects (>10%) of Microgynon[®] are headache, spotting and intermenstrual bleeding. Furthermore, the following undesirable effects have been observed: gastric upset, nausea, vomiting, breast tenderness, changes in body weight, changes in libido, and depression. In predisposed women, use of Microgynon[®] can sometimes cause chloasma which is exacerbated by exposure to sunlight. Women with a predisposition to pigment changes should avoid prolonged exposure to sunlight. Individual cases of poor tolerance of contact lenses have been reported with use of oral contraceptives; therefore, contact lens wearers who develop changes in lens tolerance should be assessed by an ophthalmologist. Menstrual changes associated with the use of oral contraceptives include reduction of menstrual flow and missed menstruation. Intermenstrual bleeding may occur, but normally ceases spontaneously.

Two doses of Microgynon[®] (containing 30 microgram ethinylestradiol (EE) and 150 microgram levonorgestrel (LE) per tablet) will be administered during this trial. Therefore, no undue risk is expected to trial participants.

1.4.3 Potential interaction between nintedanib and Microgynon

The major enzyme involved in biotransformation of ethinylestradiol is CYP3A4. Based on *in vitro* data, nintedanib is neither an inducer nor an inhibitor of CYP enzymes. Therefore, the co-administration of nintedanib is not expected to cause an interaction with Microgynon[®].

1.4.4 Drug induced liver injury

Although rare, a potential for drug-induced liver injury (DILI) is under constant surveillance by sponsors and regulators. Therefore, this trial requires timely detection, evaluation, and follow-up of laboratory alterations in selected liver laboratory parameters to ensure patients' safety, see also Section [5.2.10.1.4](#), adverse events of special interest.

2. TRIAL OBJECTIVES AND ENDPOINTS

2.1 MAIN OBJECTIVES, PRIMARY AND SECONDARY ENDPOINTS

2.1.1 Main objectives

The main objective is to assess the potential influence of continuous intake of nintedanib on the systemic exposure of ethinylestradiol and levonorgestrel when administered in combination, as assessed by the endpoints described in the following sections.

2.1.2 Primary endpoints

Pharmacokinetic endpoints

The following primary endpoints will be determined for ethinylestradiol and levonorgestrel based on the sampling times given in the [Flow Chart](#):

- AUC_{0-tz} (area under the concentration-time curve of the analyte in plasma over the time interval from 0 to the last quantifiable data point)
- C_{max} (maximum measured concentration of the analyte in plasma)

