Nintedanib does not induce CYP enzymes *in vitro* nor in rats *in vivo* ([U09-1731](#), [U04-2195](#)). Therefore, the likelihood of nintedanib causing a relevant pharmacokinetic drug-drug interaction on oral contraceptives by induction of their metabolism that would lead to a loss of the pharmacodynamic action of these drugs is considered to be very low. Due to teratogenic potential of nintedanib the EMA DDI guidance from 2012 nevertheless requires to perform a clinical study to investigate the potential effect of nintedanib on the PK of oral contraceptives.

Residual Effect Period

The Residual Effect Period (REP) of nintedanib is 7 days

The Residual Effect Period (REP) of Microgynon[®] is 3 days.

The REP is the period after the last dose with measurable drug levels and/or pharmacodynamic effects still likely to be present.

Data from non-clinical and toxicology studies

In rats, embryo-foetal lethality and teratogenic effects were observed at exposure levels below human exposure at the Maximum Recommended Human Dose (MRHD) of 150 mg twice daily. Effects on the development of the axial skeleton and on the development of the great arteries were also noted at subtherapeutic exposure levels.

In rabbits, embryo-foetal lethality and teratogenic effects were observed at an exposure approximately 3 times higher than at the MRHD but equivocal effects on the embryo-foetal development of the axial skeleton and the heart were noted already at an exposure below that at the MRHD of 150 mg twice daily.

In a pre- and postnatal development study in rats, effects on pre- and post-natal development were seen at an exposure below the MRHD.

A study of male fertility and early embryonic development up to implantation in rats did not reveal effects on the male reproductive tract and male fertility.

In rats, small amounts of radiolabelled nintedanib and/or its metabolites were excreted into the milk ($\leq 0.5\%$ of the administered dose).

Data from clinical studies

The clinical efficacy of nintedanib has been studied in over 1400 patients with IPF in one Phase II dose finding trial (TOMORROW) including four different doses of nintedanib, and

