2.1.3 Secondary endpoint

Pharmacokinetic endpoint

The following secondary endpoint will be determined for ethinylestradiol and levonorgestrel based on the sampling times given in the Flow Chart:

- AUC_{0-∞} (area under the concentration-time curve of the analyte in plasma over the time interval from 0 extrapolated to infinity)

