5.3 DRUG CONCENTRATION MEASUREMENTS AND PHARMACOKINETICS

5.3.1 Assessment of pharmacokinetics

C_{max} , AUC_{0-tz} , and $AUC_{0-\infty}$ for ethinylestradiol and levonorgestrel will be evaluated to assess whether or not nintedanib has an influence on ethinylestradiol and/or levonorgestrel exposure. Pharmacokinetic plasma sampling will occur according to the [Flow Chart](#).

After completion of the trial, the plasma samples may be used for further methodological investigations, e.g. for stability testing, assessment of metabolites. However, only data related to the analyte and/or its metabolite(s) including anti-drug antibodies (if applicable) will be generated by these additional investigations. The study samples will be discarded after

completion of the additional investigations but not later than 5 years upon the final study report has been signed.

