7.3.2 Secondary endpoint analyses

The secondary PK parameters described in Section [2.1.3](#) will be analysed as described for the primary PK endpoints.

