7.7 DETERMINATION OF SAMPLE SIZE

It is planned to obtain 14 patients who can be analysed with regard to the pharmacokinetic parameters in both periods. This sample size is considered sufficient to achieve the aims of this exploratory trial. Considering possible drop outs due to safety or administrative reasons

and the potential intake of co-medication that might interfere with pharmacokinetics of Microgynon[®] (see 4.2.2.1) a total of approximately 24 patients may be enrolled (see Section 3.3.4.1). If there are less than 14 patients evaluable in both periods, the CT Leader together with the Trial Pharmacokineticist and the Trial Statistician are to decide if and how many patients will have to be enrolled in addition.

The observed intra-individual coefficient of variation (gCV) for EE and LE in previous trials in healthy volunteers (U12-1031; U09-1393; U07-1867; U03-3408; U09-1853) was roughly up to 20% for C_{max} and 15% for AUC_{0-tz} or AUC_{τ,ss}, respectively. Assuming a gCV of 20% and given the chosen sample size of 14 patients, the precision of the two-sided 90% confidence interval of the ratio test/reference (AUC and C_{max}) will be approximately 1.19 (upper confidence limit (CL) / point estimate); if only 12 patients will be evaluable in both periods, the precision would still be approximately 1.21. Table 7.7: 1 provides an overview of the 90% confidence intervals that are expected with 95% probability, for possible scenarios of the gCV and intra-patient ratios (test/reference) (T/R), and assuming available data for both periods.

Table 7.7: 1 Precision that can be expected with 95% tolerance probability and illustrative two-sided 90% confidence intervals around the ratios of geometric means (T/R) for different gCVs in a fixed sequence trial

gCV	N	Precision upper CL/ lower CL	Precision upper CL/ point estimate	T/R [%] ¹	90% CI [%]
20%	8	1.702	1.305	70%	(53.65, 91.33)
				80%	(61.32, 104.37)
				90%	(68.98, 117.42)
				100%	(76.65, 130.47)
	10	1.561	1.249	70%	(56.03, 87.45)
				80%	(64.03, 99.95)
				90%	(72.04, 112.44)
				100%	(80.04, 124.93)
	12	1.475	1.214	70%	(57.65, 85.00)
				80%	(65.88, 97.15)
				90%	(74.12, 109.29)
				100%	(82.35, 121.43)
	14	1.416	1.190	70%	(58.83, 83.29)
				80%	(67.23, 95.19)
				90%	(75.64, 107.09)
				100%	(84.04, 118.99)
16	1.373	1.172	70%	(59.74, 82.02)	
			80%	(68.28, 93.74)	
			90%	(76.81, 105.45)	
			100%	(85.35, 117.17)	

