7.5.2 Secondary endpoints

Analysis of relative exposure on the basis of the secondary endpoint will be performed in the same way as for the primary endpoints.

See [Section 7.4](#) of this TSAP for details regarding exclusion of PK parameters and plasma concentrations.

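### Levonorgestrel is sampled to only about 1.9 half-lives, so its primary AUC0-tz ratio depends on where tz falls in each period; the SAP should add a same-window sensitivity analysis.

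*Protocol*

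**What the plan says.** Protocol 2.1.2 makes Cmax and AUC0-tz primary for both analytes and defines the latter as the "area under the concentration-time curve of the analyte in plasma over the time interval from 0 to the last quantifiable data point". Protocol 2.1.3 adds one secondary endpoint, AUC0-inf: "area under the concentration-time curve of the analyte in plasma over the time interval from 0 extrapolated to infinity".

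On sampling, the Flow Chart and its PK-day tables place the last EE/LE sample at 47:55 h after Microgynon in both periods, preceded by samples at 23:55 h and 11:55 h. Protocol 1.2.3 states: "The terminal half-life of levonorgestrel is approximately 25 h". It also describes LE as losing little on first pass.

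On late values, Protocol 7.5.3 and SAP 6.6 set values below quantification (BLQ) to zero in the lag phase and ignore them elsewhere in the profile. tz can therefore differ between a patient's two periods.

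On analysis, Protocol 7.3.2 says the secondary parameters "will be analysed as described for the primary PK endpoints". SAP 7.5.2 agrees: "Analysis of relative exposure on the basis of the secondary endpoint will be performed in the same way as for the primary endpoints". Protocol 5.3.1 names Cmax, AUC0-tz and AUC0-inf together as the parameters that "will be evaluated to assess whether or not nintedanib has an influence on ethinylestradiol and/or levonorgestrel exposure". Protocol 7.2 plans no confirmatory test, only ratios with 90% confidence intervals.

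**The concern.** Protocol 3.2 gives the purpose as ruling out induction, which acts on clearance. For a drug with little first-pass loss, higher clearance shows mainly as a faster decline after the peak. Cmax barely registers that, and a curve cut at 1.9 half-lives omits part of it. With equal tz, the primary AUC ratio is pulled toward 1.

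Faster decline also makes the 48 h sample more likely to be BLQ in Period 2 alone. The Period 2 area then stops at 24 h while the Period 1 area runs to 48 h, and the ratio is pushed well below the truth. The same happens without any interaction if the late concentrations sit near the quantification limit.

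At stake is how the LE ratios are read. No decision rule depends on them. The sections reviewed neither discuss truncation nor say how to compare periods with different tz.

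**Working it through.** **Inputs.** LE half-life 25 h (Protocol 1.2.3); last samples at about 12, 24 and 48 h (Flow Chart); gCV 20% and N = 14 (Protocol 7.7). Distribution and absorption parameters are not given and are assumed below.

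**1. The plan's own precision figure.** s = sqrt(ln(1 + 0.20²)) = 0.198. Half-width = t(0.95, 13) × s × sqrt(2/14) × sqrt(chi²(0.95, 13)/13) = 1.771 × 0.198 × 0.378 × 1.312 = 0.174, and exp(0.174) = 1.190, as in Table 7.7: 1. N = 12 gives 1.214, also as stated.

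**2. Coverage.** 47.92/25 = 1.92 half-lives.

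**3. Equal tz, closed form.** One compartment, clearance × 1.25, so the true ratio is 0.80 and the half-life goes from 25 to 20 h:

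0.80 × (1 − exp(−48 ln2/20)) / (1 − exp(−48 ln2/25)) = 0.80 × (1 − 0.189)/(1 − 0.264) = 0.881.

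The log bias is ln(0.881/0.80) = 0.096, against the planned half-width of 0.174.

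**4. Unequal tz, closed form.** The 48 h concentration in Period 2 is 0.189/0.264 = 0.72 of that in Period 1, so a BLQ value in Period 2 only is the likelier pattern under this mechanism. With Period 2 ending at 24 h and Period 1 at 48 h:

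- No effect: (1 − 0.514)/(1 − 0.264) = 0.660.
- True 0.80: 0.80 × (1 − 0.435)/(1 − 0.264) = 0.614.

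A BLQ value in Period 1 only gives the reciprocal under no effect, 1/0.660 = 1.51.

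**5. Range over assumed models.** There were 52 models with terminal half-life 25 h:

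- One-compartment, absorption rate 0.5, 1, 2 or 4 per h.
- Two-compartment, absorption rate 0.8, 1.5 or 3 per h; distribution half-life 1, 2, 4 or 6 h; terminal share of AUC 0.50, 0.60, 0.75 or 0.90.

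Areas used the Protocol's sampling times, linear up and log down, with the slope from the last three points.

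| Scenario | Quantity | True 0.80 by clearance | No effect |
|---|---|---|---|
| Both periods to 48 h | AUC0-tz | 0.824-0.885 | 1 |
| Both periods to 48 h | Cmax | 0.933-0.992 | 1 |
| Both periods to 48 h | AUC0-inf | 0.796-0.815 | 1 |
| Period 2 to 24 h, Period 1 to 48 h | AUC0-tz | 0.59-0.73 | 0.63-0.85 |
| Period 2 to 24 h, Period 1 to 48 h | AUC0-inf | not tabulated | 0.84-1.02 |
| Common window, both to 24 h | AUC to 24 h | 0.85-0.93 | 1 |

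With half-lives of 20, 25 and 30 h (156 models), AUC0-tz at equal tz reads 0.818-0.898. The extrapolated share of LE AUC0-inf is 8-28% in Period 1 and 5-20% in Period 2. A fall in bioavailability alone scales the whole curve and reads 0.80 at equal tz.

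**6. EE.** The closed form of step 3 with half-lives of 10 and 20 h (Protocol 1.2.2) gives 0.82 and 0.86, so EE is less affected.

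**7. An added 72 h tube.** Assume 10% assay noise, added to a gCV of 15%. In the worst model the noise SD of log AUC0-inf falls from 0.079 to 0.045. The step 1 formula at N = 14 then moves from 1.160 to 1.147.

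**The case against.** The plan already produces the remedy. AUC0-inf gets the same model, ratio and interval, and Protocol 5.3.1 lists it with the primary parameters. From the existing schedule it reads close to the truth. Protocol 1.2.1 rates a relevant induction effect as very unlikely, and nothing is tested. Most of this stands, and it is why the point is minor. It does not cover unequal tz: a Period 2 profile ending at 24 h distorts AUC0-tz even with no interaction, and AUC0-inf is then no longer safe either (0.84-1.02).

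Protocol 7.3 allows parameters to be set aside when data are missing at important phases of the curve. That could catch some cases, but it is a case-by-case judgement and does not mention a late BLQ value in one period.

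The model range is also open to challenge. Only the figure near 0.88 follows from the documents; the lower readings need distribution phases that the documents do not give. Section 2.2 and the PK procedure are outside the text reviewed, so percent extrapolated may already be reported.

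A reader might infer that sampling must be extended to 72 h, using the blood draws at Visit 5 and EOT. The documents do not support that as a requirement. Both draws fall at or after the end of the 3-day Microgynon residual effect period, and Protocol 1.2.1 says: "The REP is the period after the last dose with measurable drug levels and/or pharmacodynamic effects still likely to be present". That wording joins levels and effects with and/or, so it does not show that LE is unquantifiable at 72 h. No quantification limit is given, and BLQ results are quite possible. The gain is also small. The 15% used in step 7 comes from "The observed intra-individual coefficient of variation (gCV) for EE and LE in previous trials in healthy volunteers" for AUC0-tz or the steady-state AUC, not AUC0-inf, and already contains assay noise, so the absolute values are somewhat inflated.

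**Conclusion.** The point holds as a conditional one, worth considering. The LE ratio on primary AUC0-tz depends on tz. With equal tz and a purely clearance-driven effect, a true 0.80 reads about 0.88 on the Protocol's own figures and 0.82-0.90 over assumed half-lives of 20-30 h. With the 48 h sample BLQ in Period 2 only, the error reverses and is larger.

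Two stronger readings should be resisted. One is that the trial would miss a clearance-driven LE interaction. It would not, because the planned AUC0-inf recovers 0.796-0.815 when both profiles reach 48 h. The other is that AUC0-tz is always biased toward no effect. It is not: bioavailability effects at equal tz are shown in full, and unequal tz can exaggerate a fall. How often tz will differ cannot be judged from the documents.

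**What to change.** Add to SAP 7.4, for EE and LE:

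- A sensitivity analysis with the same ANOVA, ratio and 90% interval, using for each patient the AUC up to the last time point quantifiable in both periods, at most 48 h. State how small differences in actual sampling time are handled.
- A statement that this result is read beside AUC0-tz and AUC0-inf, with the number of patients whose tz differs between periods.
- Percent of AUC0-inf extrapolated, per patient and period, unless the PK procedure already requires it.

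This costs SAP text and programming only. It uses concentrations already planned, so it remains possible after sampling ends. The primary endpoint definition stays as it is, and AUC0-inf need not become co-primary.

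The downside is that a window falling back to 24 h removes the false signal but attenuates a clearance effect further (a true 0.80 reads 0.85-0.93). The analysis therefore supplements AUC0-inf and does not replace it.

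An EE/LE tube at the existing Visit 5 and EOT draws is optional. It needs a protocol amendment, may be BLQ, and improves precision only from 1.160 to 1.147 in the worst assumed model. If it were added, AUC0-tz should stay capped at the 48 h sample.
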